5.8.1.3. Report to be Generated at Final Database Lock	60
5.9. Clinical Trial Registry Analyses	60
6. References	62

7. Appendices	63
---------------------	----

Table of Contents

Table		Page
Table CGAM.5.1. Example of Missing Data Imputation Outcome		15
Table CGAM.5.2. Study Phase, Analysis Population and Corresponding Treatment Groups.....		19
Table CGAM.5.3. Patient Population with Baseline and Postbaseline Definitions by Study Phase and Type of Analysis		24
Table CGAM.5.4. Other Secondary and Exploratory Efficacy Variables and Their Derivation.....		38
Table CGAM.5.5. Baseline and Post-Baseline Definition for Treatment-Emergent Suicidal Analyses for GMB-treated Population.....		46
Table CGAM.5.6. Criteria for Treatment-Emergent, Potentially Clinical Significant and Categorical Changes and Sustained Elevation in Vital Signs and Weight.....		49
Table CGAM.5.7. Criteria for Treatment-Emergent Changes in ECG Intervals and Heart Rate		51
Table CGAM.5.8. Sample ADA Assay Results.....		53
Table CGAM.5.9. Sample Clinical ADA Interpretation Results		53
Table CGAM.5.10. Definition of Subgroup Variables		56
Table CGAM.5.11. Subgroup Analyses		56

Table of Contents

Appendix		Page
Appendix 1.	Calculation of CHW Statistics	64
Appendix 2.	Description of Important Protocol Deviations	67

3. Revision History

Statistical Analysis Plan (SAP) Version 1 on 18 December 2014.

Statistical Analysis Plan Version 2 was approved prior to first patient visit and any unblinding. The overall changes and rationale for the changes incorporated in Version 2 are as follows:

- Due to the change of the study design from 8 weeks treatment phase to 12 weeks treatment phase, the gated secondary and other secondary objectives are updated to include data up to Week 12. In addition, the baseline and postbaseline visits (weeks) are also updated to reflect this study design change. The electronic patient reported outcome (ePRO) diary will now collect the average duration and average pain for the time period rather than for each attack. Thus the derivation for mean severity and mean duration of cluster headache attack were updated.
- The approach for missing data was updated for each biweekly interval.
 - if there are ≤ 7 days with non-missing answers to cluster headache attack frequency in the biweekly interval; or 2) the primary efficacy compliance rate is $\leq 50\%$, then the weekly interval will be considered missing.
 - Otherwise, 1) if there are ≥ 8 days with non-missing answer to cluster headache attack frequency in the biweekly interval; and 2) the primary efficacy compliance rate is $> 50\%$, then the average number of cluster headache attacks across the non-missing days will be used to impute the missing days.
- The algorithm for pooling of sites was updated.
- The primary endpoint point estimate was updated so that if the sample size is increased as a result of the interim analysis, the unadjusted estimate will be used, and the median unbiased estimate and a stage-wise adjusted confidence interval (CI) for the primary efficacy analysis will be calculated to assess sensitivity of the point estimate.
- Electronic patient reported outcome diary compliance was updated to calculate both ePRO diary primary efficacy compliance rate and overall ePRO diary compliance rate.
- Addition of analysis for change from baseline in total weekly dose of sumatriptan subcutaneous, sumatriptan nasal spray, and zolmitriptan nasal spray separately as well as combined.

Statistical Analysis Plan Version 3 was approved prior to first interim analysis (IA1). The changes incorporated in Version 3 are as follows:

- Post-treatment follow-up phase safety analyses will have only 1 baseline.
- A section on protocol violations to be identified was added.
- Sensitivity analyses were updated, to be consistent with other Phase 3 studies of LY2951742.

- Infections section will only deal with upper respiratory tract infections; analyses were updated to be consistent with other Phase 3 studies of LY2951742.
- For Columbia-Suicide Severity Rating Scale (C-SSRS), 1 bullet was split into 2 to enhance readability, and baseline definition for improvement from baseline analysis was clarified.
- Criteria for sustained elevation in diastolic blood pressure (DBP) was changed to be consistent with the single-time-point analysis.
- Analyses of elevations in hepatic laboratory tests were clarified, and an additional subset was added.
- An additional criteria threshold for corrected QT (QTc) interval increase was added.
- Immunogenicity analyses were updated, to be consistent with other Phase 3 studies of LY2951742.
- An additional subgroup analysis category, for age, was added.
- Some minor corrections and clarifications were made.

Statistical Analysis Plan Version 4 is approved prior to IA2 (the interim analysis for primary efficacy endpoint assessment after all patients complete double-blind phase, which is the first unblinding to study team). The updates were made mainly for incorporating the recent learnings from migraine data or for consistency across the galcanezumab program. The changes incorporated in Version 4 are summarized as follows:

- LY2951742 was replaced by galcanezumab in the body of the SAP.
- Consistent with the primary endpoint and analysis methodology for the pivotal migraine studies, the primary endpoint was updated to be the overall treatment effect over the 12-week double-blind treatment phase, rather than the treatment effect at the single time point, weeks 3/4. This update will enable the primary efficacy endpoint to assess the sustained effect of galcanezumab over 3 months in patients with chronic cluster headache.
- Due to the update to the primary endpoint, the gated secondary objective to assess the efficacy of galcanezumab 300 mg in reducing the frequency of weekly cluster headache attacks from baseline to the sequential gated time points of Weeks 5/6, 7/8, 9/10, and 11/12 to evaluate the sustained effect of galcanezumab is removed, and it is replaced with the following gated secondary objective: to assess the efficacy of galcanezumab 300 mg compared with placebo in the estimated mean proportion of patients with a 50% or greater reduction from baseline in the weekly frequency of cluster headache attacks during the 12-week double-blind treatment phase.

- In Section 5.4.1.2, minor modifications were made to clarify the approach to split the post-baseline data into biweekly intervals. In addition, the exploratory endpoints for severity and duration of cluster headache attack pain, and for the abortive medications were updated to clarify the research questions and the derivations were modified correspondingly.
- In Section 5.5.1.1 and 5.5.8.3, it was clarified that, for other secondary and exploratory efficacy measures that are not derived from cluster headache frequency, the baseline average daily cluster headache attack frequency category variable is included in the statistical analysis models.
- The list of analyses for other secondary and exploratory efficacy variables were updated in Table CGAM.5.4. Last observation carried forward (LOCF) analysis for some exploratory variables was removed. Corrections were made to include week 15/16 for ePRO analyses for Study Phase (SP) IV.
- Since no partially completed diary can be submitted, the ePRO diary primary efficacy compliance and overall ePRO diary compliance are combined into one diary compliance calculation in Section 5.5.6.
- In Section 5.5.1 and Table CGAM.5.2, safety population and modal treatment description for SP III were added for safety analyses since it is more appropriate to present safety results by the actual treatments patients received; post-treatment population is removed since the safety analyses for SP V were removed.
- The safety analyses for SP IV in open-label population and for SP V in post-treatment population were replaced by analyses during galcanezumab (GMB)-treated time and GMB-treated time plus post-treatment time in the GMB-treated population since it was determined that having overall estimates of safety outcomes across study phases was more medically useful than having estimates by study phase. Due to this change, the patient population, baseline, and postbaseline definitions for safety parameters in Table CGAM.5.3 and all related safety sections were updated correspondingly.
- Terminologies and identification criteria were updated for adverse events of special interest (AESI) for the consistency across the galcanezumab program.
- In Section 5.5.9.1.3, detailed baseline and postbaseline definition for vital signs and weight were added. The patient populations for analysis that do not satisfy treatment emergent definition were removed from Table CGAM.5.6.
- In Section 5.5.9.1.4, the parameter of large clinical trial population based QT correction (QTcLCTPB) was removed for electrocardiogram (ECG) analysis. The detailed baseline and postbaseline definitions for ECG were added.
- In Section 5.5.9.2, for continuous safety measures, box-whisker plots with summary tables for SP III replaced LOCF and repeated measures analysis.
- Section 5.5.9.1.6 of immunogenicity was updated to clarify definitions and modify analyses to focus on evaluation of the incidence of baseline ADA and treatment-emergent ADA.

- Subgroup analysis for safety endpoints were removed due to small size of the study. A few subgroup variables for the efficacy endpoint were removed due to small size in subgroups.
- In Section 5.8, reports to be generated were updated to reflect that analyses from all study phases specified in this SAP will be performed at IA2 instead of only performing analyses for SP III. However, the analyses conducted for SP III will be deemed final since all patients will complete SP III at IA2. The analyses using data from SP IV and SP V will be rerun and updated when the completed data are available at the final database lock.
- An appendix of important protocol deviations was added.
- Other minor corrections, modifications, and clarifications were made.

Statistical Analysis Plan Version 5 has been approved prior to IA2 (the interim analysis for primary efficacy endpoint assessment after all patients complete double-blind phase, which is the first unblinding to study team). There is no modification to the primary analysis methodologies for the primary, key secondary, and other secondary efficacy endpoints. The changes incorporated in Version 5 are summarized as follows:

- In Section 5.4.1.2, the exploratory endpoint for cluster headache attack duration was modified from “average weekly cluster headache attack minutes per attack for the remaining cluster headache days” to “weekly total cluster headache attack duration.” An exploratory responder endpoint for the weekly total cluster headache attack duration that is defined as 30% or greater reduction is also added.
- In Section 5.5.9.1.2, removed the requirement of needing at least 4 events occurred in at least 1 treatment to display p-value.
- In Table CGAM.5.6, added additional patient populations for analysis of treatment-emergent, potentially clinically significant changes and sustained elevation in vital signs.
- In Section 5.5.10, additional subgroup variables were added for subgroup analysis.
- In Appendix 1, added additional information to explain how to obtain z test statistics from the chi-square test p-values, and made minor clarifications and corrections in the formulas in Table APP1.2.
- CCI
- In the table of Description of Important Protocol Deviations in Appendix 2, updated the data source of the Important Protocol Deviations (IPDs) to only display the final data source for the IPD analysis. Two new IPDs were added and 1 IPD was removed.

4. Study Objectives

Note: This study employs nominal 14-day intervals from which an average weekly cluster headache attack frequency is calculated.

4.1. Primary Objective

The primary objective is to assess the efficacy of galcanezumab 300 mg administered every 30 days compared with placebo in reducing the frequency of weekly cluster headache attacks in patients with chronic cluster headache. The primary outcome measure is the weekly cluster headache attack frequency. The primary endpoint is the overall mean change from baseline in weekly cluster headache attack frequency during the 12-week double-blind treatment phase with galcanezumab 300 mg compared with placebo.

4.2. Secondary Objectives

4.2.1. Gated Objective

- To assess the efficacy of galcanezumab 300 mg compared with placebo in the estimated mean proportion of patients with a 50% or greater reduction from baseline in the weekly frequency of cluster headache attacks during the 12-week double-blind treatment phase.
- To assess the efficacy of galcanezumab 300 mg compared with placebo in the proportion of patients meeting sustained response through Week 12. For this analysis, sustained response is defined as a 50% or greater reduction in the weekly cluster attack frequency from baseline to Weeks 3/4 and maintained at Weeks 5/6, Weeks 7/8, Weeks 9/10, and Weeks 11/12.

4.2.2. Other Secondary Objectives

- To assess whether galcanezumab 300 mg is superior to placebo on the following:
 - Mean change in the weekly cluster headache attack frequency from baseline to each 2-week interval through Week 12.
 - The proportion of patients with a 50% or greater reduction in the weekly frequency of cluster headache attacks from baseline at each 2-week interval through Week 12.
 - The proportion of patients with a 30% or greater reduction in the weekly frequency of cluster headache attacks from baseline at each 2-week interval through Week 12.
 - Proportion of patients reporting a score of 1 (“very much better”) or 2 (“much better”) on the Patient Global Impression of Improvement (PGI-I) at Month 1, Month 2, and Month 3.
- To compare galcanezumab with placebo on the following safety and tolerability measures:
 - spontaneously reported treatment-emergent adverse events (TEAEs)

- serious adverse events (SAEs)
- adverse events leading to discontinuation
- suicidal ideation and behaviors assessed by solicited questioning using the C-SSRS.
- To assess the development and consequences of anti-drug antibodies (ADA) to galcanezumab in patients exposed to galcanezumab; to provide samples for subsequent evaluation of neutralizing ADA (Nab).
- To evaluate the pharmacokinetics (PK) of galcanezumab.

4.3. Exploratory Objectives

To assess whether galcanezumab is superior to placebo as measured by:

- Proportion of patients randomized to galcanezumab meeting “very much better” or “much better” on the PGI-I at Month 9 and Month 15.
- Mean change in the weekly number of times of abortive medication use from baseline to each 2-week interval through Week 12 comparing galcanezumab with placebo.
- Change in percentage of times using oxygen from baseline for each 2-week interval through Week 12 comparing galcanezumab with placebo.
- Change in percentage of times using trip tan from baseline for each 2-week interval through Week 12 comparing galcanezumab with placebo.
- Change in percentage of times of using acetaminophen/paracetamol or nonsteroidal anti-inflammatory drugs (NSAIDs) from baseline for each 2-week interval through Week 12 comparing galcanezumab with placebo.
- Responder analyses of galcanezumab compared with placebo from baseline to each 2-week interval through Week 12 for the proportion of patients meeting:
 - a 75% or greater reduction in the weekly cluster headache attack frequency
 - a 100% reduction in weekly cluster headache attack frequency
- Mean change from baseline to each 2-week interval through Week 12 in the cluster headache attack average weekly pain severity based on 5-point pain severity scale comparing galcanezumab with placebo

● CCI

● CCI

5. A Priori Statistical Methods

5.1. Study Design

Study CGAM is a Phase 3 multi-center, outpatient, randomized, double-blind, placebo-controlled study of galcanezumab 300 mg for the prevention of chronic cluster headache. The study has 5 study phases (SP):

- SP I (screening/washout phase)
- SP II (pre-randomization diary phase)
- SP III (double-blind treatment phase)
- SP IV (optional open-label extension phase)
- SP V (post-treatment follow-up phase)

5.2. Determination of Sample Size

The study is planned to have a minimum of approximately 162 patients randomized 1:1 to placebo or galcanezumab 300 mg with the opportunity to increase the final sample size at an interim analysis if indicated in order to maintain a well powered study. To preserve blinding, details of the sample size and power calculations are omitted from this SAP and are provided in a separate document to the Ethical Review Board (ERB).

5.3. Randomization and Treatment Assignment

At Visit 3, eligible patients will be randomized in a 1:1 ratio to double-blind placebo or galcanezumab 300 mg respectively. To achieve marginal balance of treatment assignments for the factors of gender, verapamil use (yes/no), average daily attack frequency (≤ 4 attacks per day, > 4 attacks per day) and investigative site, randomization will be conducted with a dynamic allocation (minimization) method (Pocock and Simon 1975) with target probability of 0.8. Assignment to treatment groups will be determined by a computer-generated random sequence using an interactive web-response system (IWRS).

5.4. Endpoints

5.4.1. Efficacy Endpoint

5.4.1.1. Cluster Headache Attack Primary Endpoint

Patient-Rated Daily electronic patient reported outcome (ePRO) Diary: Patients will be asked to record the number of cluster headache attacks in their daily ePRO diary during SP II and SP III, which is used to derive the primary efficacy endpoint. Patients who enter SP IV will continue to diary on a daily basis through Visit 11. Information regarding abortive medication use, cluster headache attack duration on average, and cluster headache attack pain severity on average will also be recorded. Pain severity will be rated using a 5-point pain scale, where 0=no pain, 1=mild pain, 2=moderate pain, 3=severe pain, and 4=very severe pain (The Sumatriptan Cluster

Headache Study Group 1991). Patients should record all cluster attacks regardless of attack duration.

5.4.1.2. Derived Variables for Cluster Headache Attacks

In Study I5Q-MC-CGAM (CGAM), for primary measure of cluster headache attacks, the daily data for each patient (including last 14 days in the eligibility report [pre-randomization diary phase]), 12 weeks of daily data during double-blind treatment phase and 4 weeks of daily data during open-label extension phase) will be converted into 9 roughly 14-calendar day intervals: the baseline 14-day interval, Weeks 1/2, 3/4, 5/6, 7/8, 9/10, 11/12, 13/14, and 15/16. Each day, the patient may report zero, one, or multiple cluster headache attacks. Any ePRO diary data reported beyond the protocol defined collection period will not be used for statistical analysis.

The approach to split the post-baseline data into biweekly intervals is done as follows:

- First, post-baseline daily data during double-blind treatment phase will be split into Weeks 1 through 4, 5 through 8, and 9 through 12 using first, second, and third injection dates. All data greater than or equal to first injection date and less than second injection date will be considered as Weeks 1 through 4; all data greater than or equal to second injection date and less than third injection date will be considered as Weeks 5 through 8; all data greater than or equal to third injection date will be considered as Weeks 9 through 12.
- Secondly, the data within Weeks 1 through 4 will be split into Weeks 1/2 versus 3/4 using calendar days. In other words, the first injection date will be considered as Day 1, then Days 1 to 14 will be Weeks 1/2; Day 15 to the date before the second injection will be Weeks 3/4.
- Thirdly, the data within Weeks 5 through 8 will be split into Weeks 5/6 vs 7/8 using calendar days. In other words, the second injection date will be considered as Day 1, then Days 1 to 14 will be Weeks 5/6; Day 15 to the date before third injection date will be Weeks 7/8.
- Lastly, the data within Weeks 9 through 12 will be split into Weeks 9/10 versus Weeks 11/12 using calendar days. In other words, the third injection date will be considered as Day 1, then Days 1 to 14 will be Weeks 9/10; Day 15 to the day before double-blind phase completion date (which is also the first injection date if the patient continues into open-label phase) will be Weeks 11/12.
- During open-label phase, the data from first injection date to the day before second injection date of open-label phase will be considered as Weeks 13 through 16. The first injection date in open-label phase will be considered as Day 1, then Days 1 to 14 will be Weeks 13/14; Day 15 to the day before next injection date will be Weeks 15/16.

For each biweekly interval, the following missing data imputation method will be used:

- 1) If there are ≤ 7 days with non-missing answer to cluster headache attack frequency in the biweekly interval; or 2) the diary compliance rate is $\leq 50\%$, then the biweekly interval will be considered missing;
- Otherwise, 1) if there are ≥ 8 days with non-missing answer to cluster headache attack frequency in the biweekly interval; and 2) the diary compliance rate is $> 50\%$, then the average number of cluster headache attacks across the non-missing days will be used to impute the missing days. Furthermore, the total cluster headache attack frequency during the biweekly interval will be calculated as the average number of cluster headache attacks across non-missing days times the actual number of calendar days within each biweekly interval.

Then to estimate a weekly outcome of the total frequency for an efficacy measure from ePRO diary, the biweekly interval results will be adjusted to 7-day (weekly) interval by multiplying $\frac{x}{2}$, where “x” is the actual number of calendar days within each biweekly interval. The purpose of adjusting to weekly interval is to be able to report the outcome as weekly frequency. Lastly, the change from baseline to Weeks 1/2, 3/4, 5/6, 7/8, 9/10, 11/12, 13/14, and 15/16 will be derived.

An example of missing data imputation is described below in [Table CGAM.5.1](#).

Table CGAM.5.1. Example of Missing Data Imputation Outcome

	Example 1			Example 2		
	Number of Calendar Days	Number of Days with Non-Missing Answer to Cluster Headache Attack Frequency	Missing Data Imputation	Number of Calendar Days	Number of Days with Non-Missing Answer to Cluster Headache Attack Frequency	Missing Data Imputation
Weeks 1/2	14	14	*a	14	8	*b
Weeks 3/4	13	8	*b	13	7	*d
Weeks 5/6	14	6	*c and *d	14	14	*a
Weeks 7/8	17	8	*c	13	8	*b
Weeks 9/10	14	14	*a	14	14	*a
Weeks 11/12	13	6	*c and *d	16	8	*c

*a No imputation.

*b The average number of cluster headache attacks across the non-missing days will be used to impute the missing days.

*c Set to missing (diary compliance $\leq 50\%$).

*d Set to missing (number of days with non-missing answer to cluster headache attack frequency ≤ 7).

The same missing data imputation approach will also be applied to secondary and exploratory efficacy measures that are derived from ePRO data.

Gated secondary, other secondary and exploratory efficacy measures will be derived for each patient for each 14-day interval as follows:

- A 30%, 50%, 75%, and 100% responder is defined as any patient who has a $\geq 30\%$, $\geq 50\%$, $\geq 75\%$ and $=100\%$ reduction in the weekly number of cluster headache attacks in a 14-day interval relative to baseline interval. For 30%, 50%, 75%, and 100% responder definition, percentage reduction from baseline will be calculated as:

$$\frac{100 \times (-1) \times (\text{weekly # of cluster headache attacks at week X} - \text{weekly # of cluster headache attacks at baseline Interval})}{\text{weekly # of cluster headache attacks at baseline interval}}$$

- Change from baseline for the remaining cluster headache attack days:
 - Change from baseline in the cluster headache attack average weekly pain severity for the remaining cluster headache attack days will be derived at each 2-week interval through Week 12. For the calculation of mean severity of cluster headache attack, severity has 5 categories: 0 = no pain, 1 = mild pain, 2 = moderate pain, 3 = severe pain, and 4 = very severe pain. The mean severity for the remaining cluster headache attack days for each interval will be calculated as:

$$\frac{\text{Sum of average cluster headache severity per day during the interval}}{\text{\# of days with cluster headache attack during the interval}}$$

If there is zero cluster headache attack within the interval, then the mean severity of cluster headache attack for that interval will be considered not applicable hence missing at the interval for analyses purpose.

- Change from baseline in weekly total cluster headache attack duration will be calculated for each biweekly interval. Average duration of cluster headache attacks during a 24-hour period was asked in the ePRO diary. Patients were instructed to round up to the next duration selection with following choices: 15 minutes, 30 minutes, 1 hour, 2 hours, 3 hours, >3 hours. If the duration is >3 hours, then 4 hours will be imputed for the calculation of the total cluster headache attack duration. The total cluster headache attack duration for each interval will be calculated as the summation of the average duration of cluster headache attack multiplied by the number of cluster headache attacks in the day during the interval. If the total duration is more than 24 hours for a day, it will be set to 24 hours.
- The proportion of patients with a 30% or greater reduction from baseline in the weekly total cluster headache attack duration will be calculated for each biweekly interval.
- Change from baseline in weekly number of times of using oxygen as abortive medication at each interval will be calculated.

- Change from baseline in weekly number of times of using oral triptan, sumatriptan nasal spray, or zolmitriptan nasal spray as abortive medication at each interval will be calculated.
- Change from baseline in weekly number of times of using sumatriptan Sc as abortive medication at each interval will be calculated.
- Change from baseline in weekly number of times of using acetaminophen/paracetamol or NSAIDs as abortive medication at each interval will be derived.
- Change from baseline in number of times using oxygen as abortive medication per cluster headache attack at each interval will be derived. The endpoint at each interval will be calculated as follows:

$$\frac{\text{Total number of times using of oxygen during the interval}}{\# \text{ of cluster headache attack during the interval}}$$

- Change from baseline in number of times using oral triptan, sumatriptan nasal spray, or zolmitriptan nasal spray as abortive medication per cluster headache attack at each interval will be derived. The endpoint at each interval will be calculated as follows:

$$\frac{\text{Total number of times using the specified types of triptan during the interval}}{\# \text{ of cluster headache attack during the interval}}$$

- Change from baseline in number of times using sumatriptan Sc as abortive medication per cluster headache attack at each interval will be derived.
- Change from baseline in number of times using acetaminophen/ paracetamol or NSAIDs as abortive medication per cluster headache attack at each interval will be derived. The endpoint at each interval will be calculated as follows:

$$\frac{\text{Total number of times using of acetaminophen/paracetamol or NSAIDs during the interval}}{\# \text{ of cluster headache attack during the interval}}$$

- Change from baseline in total weekly dose for oral triptan, sumatriptan nasal spray and zolmitriptan nasal spray combined will be derived. Total weekly dose will be calculated as follows:

$$\frac{\text{Sum of doses of oral triptan, sumatriptan nasal spray and zolmitriptan nasal spray during the interval} * 7}{\text{#####Number of nonmissing diary days during the interval}}$$

- Change from baseline in total weekly dose for sumatriptan Sc, oral triptan, sumatriptan nasal spray, and zolmitriptan nasal spray separately will be derived. Total weekly dose, respectively, will be calculated as follows:

$$\frac{\text{Sum of doses of sumatriptan Sc during the interval} * 7}{\text{\# of nonmissing diary days during the interval}}$$

$$\frac{\text{Sum of doses of oral triptan during the interval} * 7}{\text{\# of nonmissing diary days during the interval}}$$

$$\frac{\text{Sum of doses of sumatriptan nasal spray during the interval} * 7}{\text{\# of nonmissing diary days during the interval}}$$

$$\frac{\text{Sum of doses of zolmitriptan nasal spray during the interval} * 7}{\text{\# of nonmissing diary days during the interval}}$$

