5.5.8. Efficacy Analyses

5.5.8.1. Primary Outcome and Methodology

The primary analysis will be conducted by a restricted maximum likelihood-based (REML-based), mixed-effects repeated measures (MMRM) analysis using all the longitudinal observations at Weeks 1/2, 3/4, 5/6, 7/8, 9/10, and 11/12. The analysis of the primary outcome will be the main effect of treatment between galcanezumab 300 mg and placebo during the 12-week double-blind treatment phase from a repeated measures analysis on mean change from baseline in the weekly cluster headache attack frequency. This provides the average treatment effect across the 12-week double-blind treatment phase. Baseline is defined as the last 14 days in the eligibility report (pre-randomization diary phase). In addition to the primary endpoint results, the LSMeans, standard errors, along with 95% CIs for the mean change from baseline for GMB300mg and placebo at each bi-weekly interval will also be reported from the MMRM.

The model for the primary analysis will include the fixed, categorical effects of treatment, gender, verapamil use, pooled investigative site, week, and treatment-by-week interaction, as well as the continuous, fixed covariates of baseline value. An unstructured covariance structure will be used to model the within-patient errors. The Kenward-Roger (Kenward and Roger 1997) approximation will be used to estimate denominator degrees of freedom. If the model does not converge with both the Hessian and the G matrix being positive definite under the default fitting algorithm used by PROC MIXED, the Fisher's scoring algorithm will be implemented by specifying the SCORING option in SAS®. If the model still fails to converge, the model will be fit using covariance matrices of the following order specified by a decreasing number of covariance parameters until convergence is met:

- heterogeneous Toeplitz
- heterogeneous first-order autoregressive

- Toeplitz
- first-order autoregressive

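### Does the SAP convert biweekly attack totals to a weekly frequency with the wrong factor (x/2 instead of 7/x)?

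*SAP*

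**What the plan says.** SAP Section 5.4.1.2 builds the attack frequency in two steps. The interval total is "the average number of cluster headache attacks across non-missing days times the actual number of calendar days within each biweekly interval". Then "the biweekly interval results will be adjusted to 7-day (weekly) interval by multiplying $\frac{x}{2" (x over 2 in the text as supplied). Here x stands for the true length of the interval in calendar days, and the aim given is a weekly outcome. The note that opens the SAP objectives gives the same scale: "This study employs nominal 14-day intervals from which an average weekly cluster headache attack frequency is calculated".

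The intervals differ in length. For baseline, "Baseline is defined as the last 14 days in the eligibility report (pre-randomization diary phase"). After the first injection, "Days 1 to 14 will be Weeks 1/2; Day 15 to the date before the second injection will be Weeks 3/4", and later dosing cycles follow the same pattern. The second interval of each cycle therefore varies with visit dates.

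For triptan doses, the same section scales to a week explicitly. For example, "Sum of doses of sumatriptan Sc during the interval" is multiplied by 7 and divided by the number of non-missing diary days.

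**The concern.** Multiplying a total that already contains x by x/2 leaves a quantity proportional to x squared. Baseline is 14 days, while the second interval of a cycle is usually longer, so the factor would not cancel in change from baseline or in percent reduction. The derived variable feeds the primary MMRM, both gated endpoints, and the 30%, 50% and 75% responder analyses. Patients with no change could appear to worsen in Weeks 3/4, 7/8 and 11/12, which are three of the five intervals used for sustained response. The 50% threshold would then move with visit timing. A fault of that kind in the primary derivation would be serious, so the fraction deserved a check.

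**Working it through.** **Inputs.** Let m be mean attacks per non-missing day and x the calendar days, so the interval total is T = m·x (SAP 5.4.1.2). Baseline and the first interval of each cycle have x = 14. With dosing every 30 days (Protocol 9.5) the second interval is 30 − 14 = 16 days. The study schedule (Protocol Attachment 1: +5/−2 days, at least 28 days apart) gives 28 − 14 = 14 to 35 − 14 = 21. Table CGAM.5.1 in the SAP uses 13, 14, 16 and 17.

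**The plan's own example.** All 12 flags in Table CGAM.5.1 reproduce from the stated rules. For instance, 8/17 = 47.1% and 8/16 = 50.0% fail the compliance rule, 7 of 13 days fails the day-count rule, and 8/13 = 61.5% is imputed. This confirms that x is the actual interval length.

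**The two factors at m = 2 (true value 7 × 2 = 14 per week).**

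| x | T = 2x | T·x/2 | T·7/x |
|---|---|---|---|
| 13 | 26 | 169 | 14 |
| 14 | 28 | 196 | 14 |
| 16 | 32 | 256 | 14 |
| 17 | 34 | 289 | 14 |
| 21 | 42 | 441 | 14 |

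Literally, an unchanged patient scores 256/196 − 1 = +30.6% at x = 16. A 50% response there would need a true fall of 1 − 0.5·(14/16)² = 61.7%, and 77.8% at x = 21. Milder readings (half the total, or x/2 applied to the daily mean) both give m·x/2. That is right at x = 14 but reads 16 instead of 14 at x = 16 (+14.3%). Only T·7/x = 7m is a weekly frequency at every x. Change from baseline is then 7(m_t − m_0) and percent reduction is 100(1 − m_t/m_0), with no x left in either.

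**Which factor does the plan describe?**

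- The target is 7 days, yet x/2 contains no 7.
- The first step multiplies by x. Bringing actual calendar days in again, in order to reach a 7-day value, makes sense only as a divisor.
- The stated aim is explicit: "The purpose of adjusting to weekly interval is to be able to report the outcome as weekly frequency".
- The weekly-dose formulas in the same section use 7 over days.
- The negative binomial sensitivity analysis (SAP 5.5.11) models raw counts with log(compliant days/14) as offset, which is also a rate per unit time.
- Eligibility requires at least 8 attacks in the baseline assessment and at most 8 per day (Protocol 8.1, criterion 3). True weekly baselines therefore run from 8 × 7/14 = 4 to 8 × 7 = 56. Under x/2 they would run from 8 × 14/2 = 56 to 112 × 14/2 = 784.

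**How reliable is the fraction as read?** Fridericia's exponent appears as 1/2 in Protocol 12.2.10.5 and SAP 5.5.9.1.4, but as 1/3 where Protocol Attachment 5 reproduces that protocol section. The only logged ECG change is removal of the other QT correction. The comparison is used here only to judge how well small fractions were read. The combined-triptan dose formula in SAP 5.4.1.2 also carries a stray run of # signs. Small formulas in this text cannot be trusted symbol by symbol.

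**The case for a change.** The strongest reply is that a misreading is likely but not proven. Turning 7/x into x/2 needs both a changed digit and an inverted fraction, which is more than one smudged character. Nor is the conversion written out elsewhere: SAP 5.5.1.2 repeats the imputation rule and refers back to 5.4.1.2 without a factor, and the protocol gives no formula. A programmer working only from the printed fraction would have nothing to correct it.

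It stands that x/2 is not a valid conversion and that the supplied text alone cannot show what the source page prints. It does not follow that the plan contains a wrong rule. The surrounding sentences define the quantity completely, and no competing definition of weekly frequency exists. Output at many times the possible maximum would be obvious in the baseline table of weekly attacks (SAP 5.5.4).

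The reach would also be narrower than feared. Weeks 1/2, 5/6 and 9/10 are normally 14 days, like baseline, so percent reduction there is exact under either factor. The 100% responder analysis is untouched, since zero stays zero. Four of the six second intervals in Table CGAM.5.1 are 13 days, where the distortion reverses. Both arms follow one visit schedule, and nothing in the documents suggests that interval lengths differ by arm.

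**Conclusion.** The concern does not hold. The algebra against x/2 is correct, but the case that the plan uses it rests on a single machine-read fraction that every neighbouring statement contradicts. A fault in reading the text is not an error in the plan. The conversion the SAP describes is interval total × 7/x. It gives 7m for any interval length, so change from baseline and the responder thresholds do not depend on visit timing, and the expected effect on the primary and gated results is nil. This rests on the assumption that the fraction is a reading fault, or at most a typographical slip not carried into programming. A look at the source page would settle which.
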